6.2 Study Design

We intend to conduct a prospective non-blinded randomized trial that compares a 1-food elimination diet (1FED) versus a 4-food elimination diet (4FED) for three months (Phase I) in a 1:1 ratio, stratified by two age groups, 6-12 and 13-17 years of age. Subsequently, non-responders to 1FED dietary elimination therapy will be treated with 4FED and non-responders to 4FED will be treated with SGC (swallowed fluticasone at a dose of 880 mcg twice a day) for 3 months (Phase II). Empiric dietary therapy interventions are as follows: 1-food elimination diet (1FED)—avoidance of milk vs. 4-food elimination diet (4FED)—avoidance of milk, egg, soy, and wheat for three months. Milk elimination for both 1FED and 4FED includes all mammal milk (i.e. goat, sheep, and cow's milk must all be eliminated). The study design is shown schematically in Figure 2.

The instructions for dietary phases will be standardized across sites by providing consensus documents that contain diet information, produced by a research Registered Dietitian who is an expert in dietary elimination in EoE. Similarly, standardized instructions for using SGC will be provided, based on our prior studies. We have chosen to use fluticasone propionate (FP) rather than budesonide in this study, given our prior work in this area, and our recent finding that high-dose fluticasone is well tolerated and highly effective, and our preliminary findings concerning esophageal transcripts that predict responsiveness to FP therapy.

The clinical trial information will be entered into a databank on www.clinicaltrials.gov maintained by the U.S. National Library of Medicine (NLM) at the National Institutes of Health (NIH).

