7.3 Phase I: Enrollment & Dietary Treatment (Week 0)

All eligible participants will be enrolled into the study at Week 0 if they meet all entry criteria and have

completed the screening procedures. If a participant is screened and enrolled within a 5 day time frame study procedures that are repeated will only be performed once. At this visit, staff members will:

- Assess eligibility (inclusion and exclusion criteria)
- Measure vitals (blood pressure, heart rate, respiratory rate, temperature), height and weight
- Administer patient and parent-reported outcome questionnaires, which will include a dietary questionnaire to measure intake of the food allergens
- Review food diary (from screening) with subject
- Assess concomitant medications and/or therapies
- Serum collection for component-resolved diagnostics (CRD) [serum IgE component testing], IgG4
- Skin testing for allergies including prick (milk, egg, wheat and soy) and patch testing (milk only).
- Randomize patients to the 1FED or 4FED diet
- Provide standardized dietary instructions for 1FED or 4FED

The participants will be encouraged to call the PI and/or study coordinator if they have any questions, concerns, adverse events, or changes in medication.

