12 STATISTICAL METHODS

12.1 Sample Size Calculation

Sample size was determined based on the primary endpoint of the trial: The overall PEES score change from pre-treatment. Based on a preliminary report¹⁸ we estimate that 40-50% of patients may respond to 1FED as our study is prospective compared with 65% response in this preliminary retrospective report and based on food reintroduction trial results³⁰. Likewise, we would expect 75% of patients to respond to 6FED based on the previously reported studies, and from this we extrapolated a projected response of 65% to 4FED, given that the 4 eliminated foods are consistently identified as the most common triggering antigens³⁰. As such, we estimate that 45% of patients will respond to 1FED and wish to detect an additional 20% increase for the 4FED (i.e. 65% response rate). A non-parametric Wilcoxon rank sum test will be applied for the primary efficacy endpoint comparison. We are assuming a difference in response rate of 45% vs 65% between the two treatment groups, and we further assume that those who respond to 1FED will naturally respond to 4FED. We also assume that those who responded will have a higher PEES score change than those who do not respond. Then the estimated probability of 4FED scores higher than 1FED is about 0.60 ($= 0.5 \times \text{prob. of response to both or neither} + 1.0 \times \text{incremental response rate from 1FED to 4FED}$). This will require 131 patients per group to reach 80% power at 0.05 test level. By accounting for a 10% early dropout rate, we propose a sample size of 146 per group, or 292 total patients to be enrolled.

12.2 Statistical Analyses: Aim 1

Demographic and patient characteristics will be summarized for the two treatment groups using mean \pm standard deviation or median [interquartile range] for continuous variables and frequency and percentages for categorical variables. Treatment comparisons will be performed using the two-sample t-test or Wilcoxon Rank sum test for continuous variables and the Fisher's Exact test for categorical variables. All tests will be conducted at $\alpha=0.05$, including the primary and secondary analyses.

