6 STATISTICAL METHODS

6.1 Statistical Analyses: Aim 1

Demographic and patient characteristics will be summarized for the two treatment groups using mean \pm standard deviation or median [interquartile range] for continuous variables and frequency and percentages for categorical variables. Treatment comparisons will be performed using the two-sample t-test or Wilcoxon Rank sum test for continuous variables and the Fisher's Exact test for categorical variables. All tests will be conducted at $\alpha=0.05$, including the primary and secondary analyses.

There was going to be two sets of analysis populations in terms of efficacy assessment, the intent-to-treat and per protocol. However, since the total enrollment has been reduced to about 50, all patients randomized to Phase I of the study who have at least one clinical observation post randomization will be considered in intent-to-treat set. Only this set of population will be included in the statistical analyses. Originally, we plan to define patients who are at least 80% compliant to dietary assignment during Phase I, and who do not have any major protocol violations as in per protocol set. Now all analyses will be based on intent-to-treat population. Patients who do drop out of the trial before the end of Phase I will have their PEES done at the time of dropout. The primary endpoint is overall PEES score change from pre-treatment to the end of Phase I. If normality assumption is approximately valid, a linear mixed effect model will be applied to the primary efficacy variable,

account for site random effect, and other potentially important covariates, e.g. gender, race, and PPI use etc. Because of non-normal nature of the scores in previous research, a Wilcoxon rank sum test may be applied to compare between two treatment groups when normality is violated.

As a secondary endpoint analysis, remission rates (as defined by the percentage of participants achieving histologic remission (eosinophils less than 15/HPF) at the end of Phase I will be analyzed in the following 3 steps.

- (1) Remission rates will be computed along with their 95% CIs for each diet group separately;

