- (2) Remission rates will be compared between the two treatment groups using the generalized linear mixed effects model with the logit link (for binary outcome) that accounts for the clustering within sites. Important covariates will be analyzed in this model including gender, race, PPI use, atopy, age, and anthropomorphic features. Treatment group comparisons for secondary endpoints will be performed using the generalized linear mixed effects model using the link that is appropriate for the endpoint (i.e. logit for binary, log for Poisson count, identity for continuous). These models will account for the clustering within sites and will include the same covariates as for the primary analysis.
- (3) The remission rate for non-responders who proceed to Phase II will be summarized separately depending on the treatment patients received during Phase I and Phase II. The 95% confidence interval for the rates will also be provided.

6.2 Statistical Analyses: Aim 2

To evaluate the ability of biomarkers and phenotypic characteristics to predict response to therapeutic intervention, multivariable logistic regression analysis may be conducted with histological evaluation of remission/no remission as the dependent variable and biomarker levels as the independent variables. Multicollinearity of the independent variables will be assessed. The area under the receiver operating characteristic curve (AUROC) will be estimated along with 95% confidence interval. This analysis will be conducted based on the remission status at the end of Phase I. It may also be repeated at the end of Phase II by including those patients who also responded to SGC.

Additionally, a correlation analysis between PEES scores and biomarkers will be performed. Spearman's correlation coefficient and its confidence intervals will be computed to further assess predictive utility for the biomarkers of interest.

Missing data will be handled in the following manner. For the primary efficacy measure of PEES, each patient is expected to complete the questionnaire; even if the patient terminates participation early (dropout) for any reason. The total PEES score is the average of 20 item scores, as long as there are at least 10 item response non-missing, as described previously. No imputation of missing total PEES will be performed. The early dropout reasons will be recorded, and rates will be assessed between treatment groups for potential patterns.

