For all other secondary efficacy and demographic variables, missing data will not be imputed. However, if a participant's biomarker panel is partially missing, multiple imputation may be applied for missing markers in predictive modeling analyses.

Heterogeneity of treatment effect is referred to as the variability in the direction and magnitude of individual or subgroup treatment effects that are non-random. Descriptive heterogeneity of treatment effect analyses will first be carried out for subgroups by gender, by study site, and by age of subject. These analyses are included in the analysis plan above for primary and secondary efficacy analyses, where proper estimates of treatment effect will be extracted. Because of the small sample size in this study, any hypothesis testing of treatment heterogeneity is considered exploratory. P-values generated from multiple comparisons are not adjusted. The goal is to identify possible heterogeneity among subgroups for further confirmation. The interaction of demographic and baseline characteristics with treatment group effects may be tested in the generalized linear mixed effects models to assess heterogeneity.

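### The primary PEES change analysis does not commit to baseline PEES or the age stratum, and its fallback is an optional unadjusted Wilcoxon test, which may give up precision at about 50 patients

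*SAP*

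**What the plan says.** SAP 6.1 and protocol 12.2 define the primary endpoint as the change in total PEES score from pre-treatment to the end of Phase I. If normality holds approximately, a linear mixed model is used that is to "account for site random effect, and other potentially important covariates, e.g. gender, race, and PPI use etc". If not, "a Wilcoxon rank sum test may be applied to compare between two treatment groups when normality is violated". Neither section gives a criterion for normality. Protocol 12.1, in sizing the trial, says something firmer: "A non-parametric Wilcoxon rank sum test will be applied for the primary efficacy endpoint comparison".

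The two variables at issue are both available:
- **Baseline PEES.** Protocol 7.3 lists among the Week 0 procedures: "Administer patient and parent-reported outcome questionnaires".
- **Age stratum.** Protocol 6.2 randomises "in a 1:1 ratio, stratified by two age groups, 6-12 and 13-17 years of age". Protocol 6.9 instead leaves the stratification parameters to the statistician.

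Age appears elsewhere in the SAP. For the remission model, SAP 6.1 says "Important covariates will be analyzed in this model including gender, race, PPI use, atopy, age, and anthropomorphic features". In the heterogeneity paragraph at the end of SAP 6.2, "Descriptive heterogeneity of treatment effect analyses will first be carried out for subgroups by gender, by study site, and by age of subject". The models for the other secondary endpoints "will include the same covariates as for the primary analysis".

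SAP 4.1 reduces enrolment from the planned 292 to around 50.

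**The concern.** The list for the primary model is a set of examples, so it does not fix what will be fitted. Baseline score is usually the strongest available predictor of a change score, and the stratification factor is the one variable that the design itself says should be respected. Neither is among the examples. The secondary models that borrow the primary covariates inherit the same open set.

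The fallback goes further. A two-group Wilcoxon test carries no baseline, no stratum and no site. Both documents say that PEES scores were non-normal in earlier research, so this route could well become the primary result. Protocol 12.1 treats it as the primary test already.

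At stake is precision in a trial that now has about one sixth of its planned patients (50/292 = 0.17). The trial is also open-label, which is a further reason to leave neither the covariates nor the test to be chosen at analysis.

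**Working it through.** **Reproducing the plan's figure.** Protocol 12.1 gives P = 0.60 (the probability that a 4FED change exceeds a 1FED change), 80% power and level 0.05. By Noether's formula, two-sided:

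N = (1.960 + 0.842)² / (12 × 0.25 × 0.10²) = 261.6, so 131 per group.

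131/0.9 = 145.6, so 146 per group and 292 in total. The stated figures reproduce. At N = 50 the same formula gives 23% power.

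**Inputs for the comparison.**
- 25 per arm: SAP 4.1 with 1:1 allocation, all patients evaluable.
- Effect: P = 0.60 as a normal shift, d = √2 × z(0.60) = 0.358 SD of change.
- Not in the documents, so assumed: correlation ρ between baseline and week-12 PEES of 0.3 to 0.7, and ratio k of week-12 SD to baseline SD of 0.8, 1.0 or 1.3.
- Age is given no prognostic effect, and there is no site effect.

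**Formula.** With baseline SD s, the variance of change is s²(1 + k² − 2kρ). After adjustment for baseline the residual variance is s²k²(1 − ρ²). The ratio is

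k²(1 − ρ²) / (1 + k² − 2kρ),

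which is (1 + ρ)/2 when k = 1 and reaches 1, meaning no gain, when kρ = 1. Multiplying by (1 + 2/45) charges for two covariates at N = 50. Power comes from the noncentral t distribution with 48 (unadjusted) or 46 (adjusted) degrees of freedom.

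**Unadjusted.** Noncentrality 0.358 × √12.5 = 1.27; power 23.7%.

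**One adjusted case, k = 1, ρ = 0.5.** Ratio 0.75 × 1.044 = 0.783; noncentrality 1.27/√0.783 = 1.43; power 28.9%.

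**All cases, after the covariate cost:**

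| k | ρ | Variance ratio | Power |
|---|---|---|---|
| 0.8 | 0.3 / 0.5 / 0.7 | 0.52 / 0.60 / 0.66 | 40% / 36% / 33% |
| 1.0 | 0.3 / 0.5 / 0.7 | 0.68 / 0.78 / 0.89 | 32.5% / 28.9% / 26.0% |
| 1.3 | 0.3 / 0.5 / 0.7 | 0.84 / 0.95 / 1.04 | 27% / 25% / 23% |

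Before the covariate cost, the k = 1.3 row is about 28%, 25.5% and 24%.

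**The rank route.** Simulation with equal SDs, P = 0.60, no site effect, 5,000 runs per cell, ρ = 0.3/0.5/0.7:
- Normal data: Wilcoxon 22.0/22.1/22.5%; rank ANCOVA on baseline and age stratum 29.5/27.1/25.5%.
- Illustrative lognormal data: Wilcoxon 22.6/23.1/22.2%; rank ANCOVA 27.9/27.1/25.1%; linear mixed model with baseline and age 21.2/18.7/16.7%.

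On the skewed data the adjusted linear model falls below the plain Wilcoxon, so adding a covariate to the linear model does not by itself deal with the fallback. On normal data with k = 1.3 and ρ = 0.7, a separate simulation gave rank ANCOVA 22.4% against Wilcoxon 22.6%: no gain.

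**Age stratum.** Protocol 6.1 plans about 50 + 120 patients aged 6-12 and 120 aged 13-17, a 59:41 split. If age shifted the outcome by an assumed 0.5 SD, omitting it would widen the confidence interval by about 3%. It belongs in the model to match the randomisation; no precision gain is claimed for it.

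**The case against.** **The list does not exclude baseline or age.** This stands. A reader might infer that the plan leaves baseline PEES out, but the wording gives examples and would permit both variables. What can be said is that it does not commit to them, and that the Wilcoxon route as described has no place for them.

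**Age and baseline characteristics are covered in the heterogeneity paragraph.** SAP 6.2 says that its subgroup analyses are part of the efficacy plan above, and that interactions with baseline characteristics may be tested. Descriptive subgroups and optional, exploratory interactions are not main-effect adjustment, so this does not close the gap.

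**The stratification factor is not settled.** This stands in part. Protocol 6.2 names two age groups and protocol 6.9 defers to the statistician, so the strata actually used need confirming.

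**The gain depends on unknown quantities.** This stands. If the week-12 SD exceeds the baseline SD and the correlation is high, there is no gain or a slight loss. If the SD falls after treatment, the gain is larger.

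**The simulation is stylised.** This also stands. PEES is a bounded 0-100 mean, and protocol 12.1 derives its effect from responder rates of 45% and 65%, not from a pure shift. With 10% dropout (22.5 per arm), the equal-SD figures fall to 21.7% unadjusted and 23.8-29.6% adjusted. The simulated site models used residual degrees of freedom, and type I error reached 6.3% with an assumed site intraclass correlation of 0.10. Power under a small-sample correction was not computed. The figures indicate direction and rough size only.

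**Conclusion.** The point holds as a failure to commit. The primary model's covariates are open, the fallback drops baseline, stratum and site, and protocol 12.1 disagrees with protocol 12.2 and SAP 6.1 on which test is primary.

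The likely consequence is some lost precision. Against about 24% unadjusted power, baseline adjustment adds about 2 to 9 percentage points at equal SDs and about 10 to 17 if the week-12 SD is 0.8 of baseline. At 1.3 times baseline it adds between nothing and about 4. All of this rests on an assumed correlation of 0.3-0.7, normal data, 25 evaluable patients per arm and P = 0.60.

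Two stronger readings are not supported. The first is that the treatment comparison is biased: allocation is randomised, and an unadjusted comparison remains valid. The second is that adjustment would rescue the trial's power: every case above stays at about 40% or less, far from 80%. The change is worth making because it uses data already collected.

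**What to change.** 1. In SAP 6.1, specify the PEES change model with diet arm, baseline PEES, the age stratum used in randomisation (confirmed against protocol 6.2 and 6.9) and the site random intercept. Close the list by stating whether gender, race and PPI use are in or out. Name a small-sample degrees-of-freedom method, for example Kenward-Roger.
2. Replace the unadjusted Wilcoxon fallback with a rank analysis adjusted for baseline PEES and age stratum, and say how site is handled. Rank ANCOVA is one option.
3. Before the database is finalised, name one of the two as primary and the other as sensitivity. Report both, with no normality test to choose between them. Either order answers this point. Give the linear model's estimate and confidence interval in PEES points in any case, because a rank model does not supply them.
4. Bring protocol 12.1 into line with protocol 12.2 and SAP 6.1.
5. In the continuous secondary models, use each endpoint's own baseline and the age stratum.

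The cost is SAP and protocol wording and about two degrees of freedom, with no new data. The downside is a slight loss of precision if the week-12 SD turns out larger than baseline and the correlation is high.

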clustering within sites and will include the same covariates as for the primary analysis. The remission rate for non-responders who proceed to Phase II will be summarized separately depending on the treatment patients received during Phase I and Phase II. The 95% confidence interval for the rates will be provided.

12.3 Statistical Analyses: Aim 2

To evaluate the ability of biomarkers and phenotypic characteristics to predict response to therapeutic intervention, multivariable logistic regression analysis will be conducted with histological evaluation of remission/no remission as the dependent variable and biomarker levels as the independent variables. Multicollinearity of the independent variables will be assessed. The area under the receiver operating characteristic curve (AUROC) will be estimated along with 95% confidence interval. This analysis will be conducted based on the remission status at the end of Phase I. It will be repeated at the end of Phase II by including those patients who also responded to SGC.

A sample size of 292 total patients will provide at least 80% power to detect an AUROC of 0.60. This calculation is based on the assumption that 161 patients (66 1FED, 95 4FED) will be in remission at the end of Phase I (and therefore not move on to phase II) and 131 patients will not be in remission (with an estimated 10% dropping out and not continuing on to Phase II).

Additionally, a correlation analysis between PEES scores and biomarkers will be performed. Spearman's correlation coefficient and its confidence intervals will be computed to further assess predictive utility for the biomarkers of interest.

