4 STUDY PARTICIPANTS

4.1 Number of Participants

A total of 292 participants between the ages of 6-17 years were to be enrolled. Because of unexpectedly slow

enrollment, the actual number of participants will be around 50 total. The DMCC at the University of South Florida Health Informatics Institute will serve as the central data management center, with CCHMC serving as the primary site and the central IRB. Additional sites include: Children's Hospital of Colorado, Riley Hospital for Children, Children's Hospital of Philadelphia, University of California at San Diego/Rady Children's Hospital, Northwestern University/Lurie Children's Hospital, Tufts Medical Center, Mt. Sinai Kravis Children's Hospital, Arkansas Children's Hospital, and the University of North Carolina.

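### The remission model in SAP 6.1 keeps the covariate list written for a 292-patient trial although about 50 patients are expected; if the list is entered in full, a true diet effect would be overstated and many fits could separate.

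*SAP*

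**What the plan says.** SAP 6.1, step (2) of the remission analysis, compares the diets with a logistic mixed model that accounts for site, and adds: "Important covariates will be analyzed in this model including gender, race, PPI use, atopy, age, and anthropomorphic features." Protocol 12.2 contains the same sentence. There it accompanied the sample size of Protocol 12.1: "By accounting for a 10% early dropout rate, we propose a sample size of 146 per group, or 292 total patients to be enrolled." SAP 4.1 now states that "the actual number of participants will be around 50 total."

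Two sentences after the list, the same step says that the secondary-endpoint models "will include the same covariates as for the primary analysis." For the primary endpoint, SAP 6.1 names gender, race and PPI use only as examples and leaves the list open. Two different covariate lists therefore apply to remission.

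The SAP adapted other parts to the smaller trial. It dropped the per-protocol set, made the Aim 2 regression optional, and called tests of heterogeneity exploratory. For remission it added step (1), Phase I rates with 95% confidence intervals for each diet. The step (2) model has no limit on covariates, no penalised or exact method, and no rule for separation or non-convergence. Missing secondary and demographic data are not imputed (SAP 6.2), so the model may use fewer than 50 patients. Randomisation is "stratified by two age groups, 6-12 and 13-17 years of age" (Protocol 6.2).

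**The concern.** Maximum-likelihood logistic regression needs enough of the rarer outcome for each parameter. When there is too little, estimates of real effects drift away from zero, model standard errors fall short of the true sampling spread, and some fits separate or do not converge. Here the sample falls to about one sixth (50/292 = 0.17) and the list does not change.

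Two things are at stake: the size of the diet effect reported for remission, and whether the prespecified fit can be obtained at all. If it cannot, the analyst must choose a reduced model after seeing the data, in an open-label trial, with two candidate lists and no fallback rule.

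**Working it through.** **1. The plan's own figure.** The plan gives "This will require 131 patients per group to reach 80% power at 0.05 test level" for a Wilcoxon test on the symptom score, with a probability of 0.60 that a 4FED score exceeds a 1FED score. Noether's formula, two-sided: N = (1.960 + 0.842)² / (12 × 0.25 × 0.10²) = 261.6, so 131 per group. Then 131/0.9 = 145.6, so 146 per group and 292 in total. The figure reproduces. It does not concern the remission model, for which the documents give no sizing.

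**2. Assumed effect.** Protocol 12.1: "we estimate that 45% of patients will respond to 1FED and wish to detect an additional 20% increase for the 4FED." OR = (0.65/0.35)/(0.45/0.55) = 2.27; log OR = 0.82.

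**3. Rarer outcome per parameter.** At 292, Protocol 12.3 expects "161 patients (66 1FED, 95 4FED) will be in remission at the end of Phase I", which leaves 131 non-remitters. At 25 per arm, non-remitters = 25 × 0.55 + 25 × 0.35 = 22.5. The SAP gives neither the coding of race nor the body measurements, so the number of columns for diet plus covariates is an assumption, taken as 7 to 12.
- N = 292: 131/7 = 18.7 down to 131/12 = 10.9.
- N = 50: 22.5/7 = 3.2 down to 22.5/12 = 1.9.

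Ten clinical sites are listed, so the site effect rests on about 5 patients per site.

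**4. Simulation at the plan's rates (true OR 2.27).** Assumptions not in the documents: covariate prevalences, and a site SD of 0.3 on the logit scale. In the table the covariates are unrelated to remission, so the inflation is small-sample bias and not a gap between conditional and marginal odds ratios. There were 4,000 trials per ML or Firth row (no site term) and 800 per mixed-model row.

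| Fit | N | Columns | Median OR | Mean SE | SD of log OR | SE/SD | 95% CI coverage |
|---|---|---|---|---|---|---|---|
| Mixed, diet and site only | 50 | 1 | 2.30 | 0.63 | 0.66 | 0.95 | 94.9% |
| Mixed | 50 | 4 | 2.55 | 0.69 | 0.75 | 0.92 | 95.3% |
| Mixed | 50 | 7 | 2.82 | 0.78 | 0.93 | 0.85 | 94.7% |
| Mixed | 50 | 10 | 3.17 | 0.91 | 1.20 | 0.76 | 93.3% |
| ML | 50 | 7 | 2.64 | 0.71 | 0.80 | 0.89 | 93.8% |
| ML | 50 | 10 | 2.82 | 0.78 | 0.94 | 0.83 | 93.2% |
| ML | 50 | 12 | 2.94 | 0.84 | 1.04 | 0.81 | 93.2% |
| Firth | 50 | 7 | 2.26 | 0.67 | 0.64 | 1.05 | 97.1% |
| Firth | 50 | 10 | 2.24 | 0.72 | 0.69 | 1.04 | 97.2% |
| ML | 292 | 10 | 2.31 | 0.25 | 0.26 | 0.97 | 94.2% |

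Across all settings, including moderately prognostic covariates, the mixed model's median OR is 2.7–2.8 with 7 columns, 3.0–3.2 with 10 and 3.0–3.3 with 12. Its SE/SD ratio is 0.82–0.89 with 7 columns and 0.72–0.84 with 10.

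**5. Fit failure.** Separation or a diverging covariate coefficient occurs in about 5% of fits with 7 columns, 35% with 10 and 60–63% with 12, against 0–0.1% at N = 292. It is usually a covariate that diverges, not diet: with 12 columns, 3,991 of 4,000 ML fits still gave a diet log OR below 8 in absolute value.

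**6. No true effect (OR 1).** ML median ORs are 0.98 to 1.03 with 7 to 12 columns. The 10-column mixed model gives 1.09, with a mean log OR of 0.043 and simulation error 0.039. Type I error is about 4–7%.

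**7. Short model.** In a separate run without site variance, diet plus age stratum gave a median OR of 2.36 (SE 0.60, SD 0.64, type I error 4.9%). Eight covariates gave 2.82 (SE 0.73, SD 0.91, type I error 6.9%). The eight-covariate model at n = 262 gave 2.33, so the cut in sample size is the cause.

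**The case against.** The strongest reply is that the size rests on a count the SAP does not give. It says the covariates will be analysed in the model, not that all enter at once, and it does not itemise the body measurements. That stands, and is why the result is a range: with 4 columns the median OR is only 2.45 to 2.55.

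Second, the harm to inference is modest. On the log scale the bias with eight covariates is log 2.82 − log 2.27 = 0.22, about a quarter of the sampling SD of 0.91. That also stands.

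Third, step (1) shows the unadjusted rates beside any model odds ratio. True, but it makes no comparison between diets. Fisher's exact test is named only in the paragraph on demographic and patient characteristics, not for remission.

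A reader might also infer more than the documents support:
- That false-positive findings become likely. Type I error and coverage move only a few points.
- That the reported standard error shrinks. It is larger than in a short model (0.73 against 0.60) and too small only relative to the true spread.
- That the long list cannot gain power. Equal rejection rates (30% and 31%) arose with covariates simulated as unrelated to outcome. With moderately prognostic ones, the full model rejected 24.3% against 21.0%, partly through type I inflation.
- That patient routing is affected. Entry to Phase II uses the local pathology read (Protocol 6.5.1.2), not this model.
- That the list was sized for 292. It was only written alongside that number.

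**Conclusion.** The concern holds in a limited form. If all listed covariates enter together at about 50 patients, and the true odds ratio is the 2.27 implied by the plan, the expected estimate is about 2.7 to 3.3. The model standard error understates the true spread by about 10 to 25%. Separation or divergence ranges from about 5% of fits to about 60%, depending on how many columns the list becomes. With no true effect the odds ratio is not biased, and error rates stay close to nominal.

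The practical harm is an exaggerated effect size, lost precision, and an unplanned choice of model if the fit fails. It is confined to one secondary endpoint, which the SAP does not rank above the others, and does not touch the primary comparison. The result depends on the assumed 7 to 12 columns, the covariate prevalences and the site variance. The unchanged list, the cut to about 50 and the conflict between the two lists can be read directly from the documents.

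**What to change.** Rewrite SAP 6.1 step (2) before the database is finalised:
- For the between-diet remission comparison, prespecify diet plus the randomisation age stratum (6–12, 13–17 years), with a site random intercept and a stated rule to drop it if the fit does not converge.
- Name the estimation method in advance, for example a Firth penalty for all binary endpoints. Do not make it depend on separation, which would leave the method to the data. State how the penalty and the site intercept are combined; the Firth runs above had no site term, so this exact combination was not simulated.
- Report the age-stratified risk difference with its 95% confidence interval beside the odds ratio.
- Move the remaining covariates to exploratory models.
- Reconcile the listed covariates with the statement that secondary models use those of the primary analysis.

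Keeping the full list under a Firth penalty also removes the inflation (median OR 2.2 to 2.3), so shortening the list is the simpler route but not the only one.

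The cost is SAP wording. Chance imbalance in the dropped covariates, and any modest gain from prognostic ones, would be handled only in exploratory models. Firth Wald intervals are slightly conservative at this size (about 97% coverage).
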